9.4 Treatments

9.4.1 Identity of Test Product

The E24377A (lot 0807) challenge strain was manufactured and supplied by Walter Reed Army Institute of Research (WRAIR), Biological Production Facility, [name], (MF 11636). Under current Good Manufacturing practice (cGMP) on August 31, 2000 and released on April 17, 2001 for use in a CHIM study. Vials of the WRAIR Production Cell Bank have been stored (at $-80^{\circ}\text{C} \pm 10^{\circ}\text{C}$) at the WRAIR Pilot BioProduction Facility since their cGMP manufacture. Further testing of the challenge strain to re-confirm its characteristics has been performed to fulfill current quality and purity standards.

For the purposes of this study, all subjects will be challenged with an inoculum prepared by the CIR JHSPH Enteric Vaccine Research Lab under the supervision of the Investigational Drug Service (IDS) from freshly plated, grown organisms. This approach was used in all previously conducted clinical studies in which the E2477A challenge strain was used. Details of the challenge strain preparation are provided in the Study Specific Procedure CIR357 – SSP 001.

9.4.2 Packaging, labelling and storage of test product

Following receipt of the frozen challenge strain from WRAIR, it will be stored at the CIR JHSPH Enteric Vaccine Research Lab in accordance with GCP and GMP requirements and will be inaccessible to unauthorized personnel.

9.4.3 Administration of Challenge strain E23477A

Each subject will receive a single administration of approximately 4×10^9 cfu of the ETEC strain E24377A (lot 0807) by mouth at baseline (Day 1).

A sodium bicarbonate buffer solution of 2 g/150 mL water will be prepared by research lab staff under the supervision of an IDS pharmacist. Each subject will drink 120 mL of this sodium bicarbonate buffer (in order to neutralize gastric acidity) one to two minutes prior to ingesting the challenge inoculum. Thereafter, subjects will drink the challenge inoculum (approximately 4×10^9 cfu) dissolved in the remaining 30 mL of buffer.

All subjects will be fasted for approximately 90 minutes before challenge and for approximately 90 minutes after challenge.

9.4.4 Product accountability

The study site will maintain a Challenge Dispensing document in each participant chart detailing the dates and quantities of challenge administration to each subject. Records will be maintained that includes subject number, administration date and amount administered. This documentation will be available to the designated CRA to verify test product accountability during the study.

Any unused challenge strain will be accounted for and destroyed as per Sponsor and SSP instructions.

9.4.5 Method of assigning subjects to treatment groups

Not applicable

9.4.6 Blinding

Not applicable

9.4.7 Emergency decoding of blinded treatment

Not applicable

9.4.8 Prior and concomitant therapy

9.4.8.1 Prohibited medications

The use of the following therapies are prohibited and exclusionary for study enrollment, as specified below:

- Recent vaccination or receipt of an investigational product (within 30 days before challenge) or intended vaccination or receipt of investigational products until 60 days after challenge, with the exception of licensed vaccine for influenza or SARS-CoV-2 vaccination that may be given up to 7 days prior to challenge.
- Regular (\geq weekly) use of laxatives, antacids, or other agents to lower stomach acidity.

- Use of any medication known to affect the immune function (e.g. corticosteroids and others) within 30 days preceding the challenge or planned use during the active study period. Use of inhaled or topical steroids may be permitted per PI discretion.
- Vaccination for or ingestion of ETEC, cholera, or LT toxin within 5 years prior to dosing.
- Use of antibiotics during the 14 days before challenge dosing or proton pump inhibitors, H2 blockers or antacids within 48 hours prior to challenge dosing.

9.4.8.2 Concomitant therapy during the study

During the study, all subjects will receive a 3-day course of antibiotics.

On the morning of Day 6 (or sooner if the subject met the criteria for early antibiotic treatment; see below), all subjects will start a 3-day course of ciprofloxacin 500 mg BID.

Subjects with an allergy to or who are unwilling to take a fluoroquinolone, may receive azithromycin 500 mg by mouth daily for three days or amoxicillin 500 mg by mouth three times daily for three days.

If, because of illness, a subject is unable to take oral antibiotics, intravenous antibiotics may be given at an appropriate dose based on weight and clinical status.

Criteria for early antibiotic treatment

Subjects meeting any of the following criteria before Day 6 will start antibiotic treatment at that time:

- Severe diarrhea as defined as >800 grams of grade 3-5 stools within a rolling 24 hour-period (see Section 9.5.3.1.2).
- Stool output consistent with moderate diarrhea for 48 hours
- Diarrhea of any severity AND 2 or more of the following symptoms: severe abdominal pain, severe abdominal cramps, severe nausea, severe headache, severe myalgias, severe arthralgia), any fever ($\geq 100.4^{\circ}\text{F}$, 38.0°C), or any vomiting
- Any fever $\geq 102.1^{\circ}\text{F}$ (39.0°C)
- A study clinician determines early treatment is warranted for any other reason

Subjects who meet the criteria for early antibiotic treatment, may be discharged from the in-patient unit earlier than anticipated upon meeting discharge criteria. Discharge criteria include at least 2 stools negative for the challenge organism, having taken at least 2 doses of antibiotics, and have no or improved symptoms.

Subjects taking any other non-antibiotic medication on a chronic basis may continue with that medication unless directed otherwise by a study clinician. All such medication will be collected on admission to the inpatient facility and will be dispensed by study staff until discharge.

Rehydration

Subjects passing grade 3-5 stools post-challenge will be asked to drink liquids, at the same volume as their stool output.

A subject may be administered IV fluids if they:

- Experience abrupt onset of diarrhea, defined as passage of an initial loose/liquid stool of >300 g, or >400 g of loose/liquid stools over 2 hours in conjunction with other symptoms, as determined by PI or designee.
- Become hypovolemic, defined as confirmed supine systolic blood pressure (BP) < 90 mmHg and associated symptoms, or significant light-headedness on standing, with a confirmed postural change in BP or pulse.
- A decrease in systolic BP or diastolic BP of > 20 mmHg or increase in pulse of > 30 beats/minute takes place when measured lying down vs. two minutes after standing.
- If determined necessary by the study provider, e.g., diarrhea with nausea/vomiting and unable to drink enough to keep up with output, or other reason.

All concomitant medications administered including antibiotics and IV fluids will be documented in the subject's medical record and in the eCRF.

Treatment for Vomiting

Treatment for severe nausea or vomiting may be needed. Participants who experience severe nausea or vomiting may be given oral or intravenous (IV) ondansetron (Zofran).

Treatment for Fever or Pain

Acetaminophen, ibuprofen, or naproxen may be used to treat fever or pain.

Other Treatments

In addition to above medications, other medications may be prescribed by the PI or designees, as needed for symptom control (e.g., heartburn), or if a medical problem arises (allergic reaction, insomnia). The most commonly utilized medication, including the indication are as follows:

Medication	Dosage	Indication	
Ondansetron oral dissolving tablet	4 mg, 8 mg once, can be repeated if not better in 30 minutes	Nausea/vomiting	
Ondansetron IV	0.15mg/kg IV x1	Vomiting	Max 16mg/dose
Acetaminophen	500 -1000 mg q 4-6 hours	Pain, fever	Max 4000 mg/day
Ibuprofen	400 – 800 mg q 6-8 hours	Pain, fever	Max 2400 mg/day
Naproxen sodium	220 – 440 mg q 12 hours	Pain, fever	Max 660 mg/day
Naproxen	250-500mg BID	Pain, fever	Max 1000 mg/day
Diphenhydramine	25-50mg oral q 6 hours PRN	Itching, insomnia	
Antacid/Antigas Liquid (Maalox, Mylanta or Generic)	As directed	Heartburn, indigestion	
Calcium Carbonate	As directed	Heartburn, indigestion	

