8.2.1 Secondary Clinical endpoints

- Severe diarrhea defined as ≥ 6 grade 3-5 stools or > 800 g of grade 3-5 stools passed within a rolling 24-hour period.
- ETEC disease severity: 3-component disease score (total score) utilizing objective signs, subjective symptoms and stool output [31].
- Incidence of diarrhea (≥ 2 grade 3-5 stools in a 24-hour period) of any severity.
- Total weight of grade 3-5 stools passed per subject over the 120-hour observation period.
- Number of grade 3-5 stools per subject over the 120-hour observation period.
- Occurrence of other ETEC Disease-specific events (malaise, loss of appetite, headache, chills, fever, nausea, abdominal pain, abdominal cramps, myalgia, arthralgia, urgency of defecation, vomiting and lightheadedness).
- Self-assessment of ETEC illness impact on daily activity at Day 6.

- Time (relative to challenge) to the first grade 3-5 stool of the first diarrhea episode.
- Time (relative to challenge) to meeting the primary endpoint (time of the stool that meets the criteria for at least moderate diarrhea).
- Requirement of early (prior to Day 6) antibiotic treatment.
- Requirement of IV fluids.
- Maximum 24-hour grade 3-5 stool output (weight).
- Maximum number (24-hour) of grade 3-5 stools.

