Note: (X) denotes optional event or procedure

Note: Procedures to be performed at an unscheduled visit are described in section 9.5.6.6. Procedures to be performed in case of an early termination are described in section 9.5.6.8.

¹ Physical exam on Day 29 optional per PI discretion.

² Pulse, sitting, lying or standing blood pressure and temperature will be measured at least 3 times daily starting on Day 1. In addition, postural blood pressure and pulse will be measured if suspicion or evidence of hypovolemia (based on assessment by clinician). Vital signs may be measured more frequently if the subject is ill.

³ Must be collected from Day -30 to Day -2.

⁴ Hematology and clinical chemistry will be performed at Day -1 if not performed within the previous 7 days.

⁵ Serum HCG pregnancy tests will be performed for people of child-bearing potential. Urine HCG will be done if serum results from admission day (Day -1) are not available.

⁶ During the inpatient and outpatient phases of the study, the interview will be used to update baseline medical history, monitor safety, and to confirm ongoing eligibility.

⁷ Subjects meeting the criteria for early antibiotic treatment per the discretion of an investigator may start this treatment prior to Day 6.

⁸ Weighing and grading ends once participant has two consecutive ETEC negative cultures, unless there is a clinical indication to continue.

⁹ Once a participant has two stools in a row negative for ETEC, their stools will no longer be cultured.

¹⁰ Quantitative stool cultures (cfu per gram of stool) will be collected on Days 2 and 4.

¹¹ To be collected before challenge if not taken on Day -1.

¹² Anticipated discharge date. Participant may be discharged earlier or later depending on when they meet discharge criteria and per PI discretion.

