9.5.3.1.2 Diarrhea definitions

Diarrhea will be rated according to the following criteria:

Mild	2-3 grade 3-5 stools in 24 hours and \leq 400 grams of grade 3-5 stools passed in a 24-hour period
Moderate	4-5 grade 3-5 stools in 24 hours or $>$ 400-800 grams of grade 3-5 stools passed in a 24-hour period
Severe	\geq 6 grade 3-5 stools in 24 hours or $>$ 800 grams of grade 3-5 stools passed in a 24-hour period

Up to 3 stools and/or rectal swabs each day will be cultured. Fecal cultures will be performed by the Enterics lab at JHSPH. Stools or swabs for culture will be taken to the JHSPH laboratory, where they will be inoculated directly onto MacConkey agar and onto MacConkey agar that had incorporated streptomycin selective for the inoculum strain. Up to 10 colonies will be agglutinated using specific antisera. The level of fecal shedding (cfu per gram of stool) will be assessed by quantitative stool cultures on Days 2 and 4 post-challenge.

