**RESTRICTED**

DOCUMENT REF.: SOP-ST-01 LAST REVISION DATE: N/A VERSION NO.: 1.0	DOCUMENT NAME: Statistical Analysis Plan		
	SPONSOR: Scandinavian Biopharma Holding AM (SBH)	PROTOCOL NUMBER: OEV-131	PROTOCOL TITLE: Pre-Study of wild type Enterotoxigenic E.coli (ETEC) Strain for Verification of a planned Challenge Dose

Subjects who meet any criterion for early antibiotic treatment will start antibiotic treatment at the time of meeting the criterion. These subjects may be discharged from the inpatient unit earlier than anticipated upon meeting all discharge criteria. Discharge criteria include passing at least 2 stools negative for the challenge organism, having taken at least 2 doses of antibiotics, and having improvement or resolution of ETEC symptoms.

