**Table 18: ETEC Illness Interventions - Full Analysis Set**

Intervention	All Subjects (N=X)		
	n	%	95% CI a
Early antibiotic treatment (prior to Day 6)	x	xx	xx.x, xx.x
Administration of IV fluids	x	xx	xx.x, xx.x
Notes: N = Number of subjects in the Full Analysis Set; n = Number of subjects who received the corresponding intervention due to ETEC illness.			
a Exact binomial confidence interval calculated via Clopper-Pearson methodology.			

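### The early-antibiotic rule is stated inconsistently on two counts, so the early-treatment rate depends on which wording the investigators follow

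*Protocol*

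**What the plan says.** **Whether treatment is compulsory.** Protocol 9.4.8.2 states: "Subjects meeting any of the following criteria before Day 6 will start antibiotic treatment at that time". SAP 2.6.4 agrees: "Subjects who meet any criterion for early antibiotic treatment will start antibiotic treatment at the time of meeting the criterion". Footnote 7 of the schedule of events (Table 1 in the protocol, and the same words in SAP Table 1) states: "Subjects meeting the criteria for early antibiotic treatment per the discretion of an investigator may start this treatment prior to Day 6".

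**What counts as severe.** The first trigger in Protocol 9.4.8.2 is "Severe diarrhea as defined as >800 grams of grade 3-5 stools within a rolling 24 hour-period", followed by a reference to Section 9.5.3.1.2. That section grades diarrhea as severe by count or by weight. So do Protocol 8.2.1 ("Severe diarrhea defined as ≥ 6 grade 3-5 stools or > 800 g of grade 3-5 stools passed within a rolling 24-hour period"), Protocol Table 8 and SAP 2.5.1. SAP 2.6.4 repeats the weight-only trigger without the cross-reference.

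**How the endpoint is counted.** Protocol 8.2.1 names the requirement of early antibiotics as a secondary endpoint. Protocol 9.7.2.1 defines it as treatment begun before Day 6. SAP Table 18 does the same in its row label and adds the note "n = Number of subjects who received the corresponding intervention due to ETEC illness".

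**The concern.** The rule decides who has the illness cut short and when. Protocol 7.3.2 says that ETEC illness generally improves within 24 hours of antibiotic therapy. The wording in force can therefore affect more than the early-treatment rate: 120-hour stool number and weight, the 24-hour maxima and the disease severity score may move with it. SAP 2.5.4.1 adds one more route. A subject whom the committee judges to have met the primary endpoint without reaching the stool thresholds is given the time of antibiotic administration as event time.

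The study exists to inform a later vaccine challenge study at the same planned dose. If two investigators can read the same rule differently, the early-treatment rate carried forward reflects an unstated choice of wording as well as the illness.

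**Working it through.** The plan gives no figure to reproduce here. The check sets the texts side by side and then looks at scale.

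**1. Compulsory or discretionary.** Each document carries both versions, and neither says which prevails.

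| Place | Subject who meets a criterion |
|---|---|
| Protocol 9.4.8.2 | will start |
| SAP 2.6.4 | will start |
| Protocol Table 1, footnote 7 | may start, at an investigator's discretion |
| SAP Table 1, footnote 7 | may start, at an investigator's discretion |

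The last criterion in the list, a clinician's decision for any other reason, does not explain the difference. It adds subjects to those treated. It does not release anyone who already meets another criterion.

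**2. Weight only, or count or weight.** Some 24-hour outputs under each definition:

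| Loose stools / weight | >800 g | ≥6 stools or >800 g | ≥4 stools or >400 g (primary) |
|---|---|---|---|
| 6 / 500 g | no | yes | yes |
| 8 / 700 g | no | yes | yes |
| 5 / 850 g | yes | yes | yes |
| 3 / 300 g | no | no | no |

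The definitions part when there are at least six stools and at most 800 g. Every such subject has already passed the primary stool threshold.

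**3. What happens next to such a subject.** Section 9.5.3.1.2 also defines moderate diarrhea by count or weight, and its weight limb runs from above 400 g to 800 g. A subject with six or more stools and output in that range fits the 48-hour moderate-output criterion if it persists. Only at 400 g or less is this unclear, which for six stools means 400 / 6 = 67 g or less each. The 48 hours must also be complete before routine treatment, five days (120 hours) after challenge, so the output must begin by about 120 − 48 = 72 hours. The any-other-reason criterion is open throughout.

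**4. Is divergence plausible?** Six stools exceed 800 g only if they average more than 800 / 6 = 133 g. Protocol Table 3 gives group means, from which:

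| Dose (cfu) | Mean output / mean loose stools | g per stool | Six stools |
|---|---|---|---|
| 6×10^8 | 585 / 4.7 | 124 | 747 g |
| 7×10^8 | 740 / 5 | 148 | 888 g |
| 3×10^9 | 1009 / 6.9 | 146 | 877 g |
| 4×10^9 | 1400 / 8 | 175 | 1050 g |

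The 800 g line lies inside the range of 747 to 1050 g. These are ratios of group means, not labelled as 24-hour values, and the first row covers 0 to 48 hours. They show that divergence can occur, not how often.

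**5. Scale.** One subject is 1 / 25 = 4.0 points or 1 / 30 = 3.3 points. As an illustration, assume about half are treated early, as in the 8 of 16 in Table 3. Three subjects handled differently would then move 12/25 = 48% (exact 95% CI 28 to 69%) to 15/25 = 60% (39 to 79%). The number three is an assumption. Values from 0 to 5 were tried, and five gives 17/25 = 68%.

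**The case against.** The weight-only trigger may be deliberate. A treatment rule need not equal an endpoint grade, the trigger states its own threshold, and the SAP repeats it without the cross-reference. Footnote 7 may be shorthand in a table, with the discretion meant for judging whether a criterion is met. Clinician judgement is also built into the list, so identical stool logs could lead to different treatment even under one agreed wording. The endpoint is descriptive, in a single-arm study without formal testing.

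Much of this is fair and limits the point. It does not remove it. The trigger offers a definition of severe diarrhea and cites a section that defines it differently, and nothing says that footnote 7 yields to the text.

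Several stronger readings are tempting and are not supported:

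- *A subject with at least six stools and at most 800 g escapes early treatment.* Step 3 shows other routes remain, clearly so above 400 g.
- *Counting treatment received contradicts an endpoint called a requirement.* Protocol 9.7.2.1 defines the requirement as treatment begun before Day 6, and SAP Table 18 follows it.
- *Table 3 implies early use of 50 to 80% here.* The 80% is 12 of 15 in a group of 20, and 15 is also the number with moderate or severe illness. If none of the other five was treated early, the rate is 12/20 = 60%.
- *Divergence will be common.* Only one of the four groups averages below 133 g per stool, at 6×10^8 cfu. The two groups nearest the planned dose average 146 and 175 g.
- *Sites will differ.* There is one site, so the issue is between investigators.
- *The rate could not be interpreted at all.* SAP Listings 6, 10 and 11 give rolling stool output, medication start day with indication, and challenge-related solicited events by day. They allow a partial reconstruction.

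**Conclusion.** Both inconsistencies stand in the current text, and neither document resolves them. The secondary rate follows the wording applied, by 3.3 to 4.0 points per subject at 30 to 25 subjects. How many subjects are involved cannot be derived from the documents. The severe-diarrhea conflict acts mainly through the timing of treatment, and it alters the rate only where no other criterion brings treatment before Day 6. Stool totals, 24-hour maxima and the severity score may also be affected. So may the event times of adjudicated cases below the stool thresholds, but only through the compulsory-or-discretionary conflict.

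A reader might infer that the primary attack rate is compromised. The severe-diarrhea conflict cannot do that by stool criteria (step 2). The other conflict could reach it only through subjects treated under the symptom, fever or clinician criteria before passing four stools or 400 g. The documents give no basis for putting a number on that, and no such effect is claimed.

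This deserves correction because the rule governs a named secondary endpoint. It is more than a clerical matter, but it is not a flaw in the primary analysis.

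**What to change.** Reconcile Protocol 9.4.8.2, its cross-reference to 9.5.3.1.2, footnote 7 of both schedules and SAP 2.6.4. One trigger list, and one statement of whether it is compulsory or discretionary, should apply throughout. Which rule is clinically right is for the sponsor and investigator. If the in-patient period is already over, the SAP and study report should state which wording was followed.

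In SAP Table 18, keep the count treated before Day 6. Beside it, show the number of subjects meeting each criterion that can be derived from the stool log and the graded solicited events, and show the remaining treated subjects as treated for another reason. Take fever from the solicited events, because Protocol 9.5.2.4 routinely brings only the Day -1 and Day 1 vital signs into the eCRF.

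The cost is a protocol and SAP clarification and a few table rows. It needs no extra subjects or procedures. The documents do not say that the eCRF records which criterion prompted treatment, so the split rests on derivation.

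### Naproxen sodium row of the supportive-medication table: the upper dose at the only listed interval totals 880 mg/day, against the row's own maximum of 660 mg/day

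*Protocol*

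**What the plan says.** Protocol 9.4.8.2 allows acetaminophen, ibuprofen or naproxen for fever or pain. Under Other Treatments it then tabulates the medications most often used, with a dosage column, an indication column and, for some rows, a maximum. Four oral pain and fever rows carry a daily maximum:

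- Acetaminophen: "500 -1000 mg q 4-6 hours", with "Max 4000 mg/day".
- Ibuprofen: "400 – 800 mg q 6-8 hours", with "Max 2400 mg/day".
- Naproxen sodium: "220 – 440 mg q 12 hours", with a maximum of 660 mg per day.
- Naproxen: 250 to 500 mg twice daily, with "Max 1000 mg/day".

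The first two rows give a range of intervals. The two naproxen rows each give one. No footnote explains how the maximum is to be combined with the dose range, and no row has a separate rule for a first dose. The SAP neither repeats nor clarifies the table. Prescribing is left to the PI or designees as needed, and 9.4.8.2 requires all concomitant medication to be recorded in the medical record and the eCRF.

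**The concern.** In the naproxen sodium row, the dosage entry permits a day that the maximum entry forbids. A prescriber who orders the upper dose at the listed interval stays inside the dosage column but goes over the daily limit printed beside it. With only one interval in the row, no longer spacing is available to bring the upper dose back under the limit.

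The situation is foreseeable. Protocol 9.5.3.1.4 lists fever, headache, myalgia and abdominal pain among the solicited ETEC events, so use of these medications should be expected during the inpatient period. What is at stake is a clear instruction to the unit and a clear basis for judging deviations. Because every dose is recorded, a day of 880 mg would be visible in the data, and the protocol gives no single answer on whether it was compliant. SAP 4.5 has deviations classified as minor or major by their impact on data quality and patient safety, so someone would have to decide the question after the fact.

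**Working it through.** **Inputs.** Dose ranges, intervals and maxima are taken from the medication table in Protocol 9.4.8.2. No outside figure is used.

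**Formula.** Daily total = dose × (24 h ÷ interval in hours). Twice daily is treated as every 12 hours.

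**Trying to reproduce the stated 660 mg from the naproxen sodium row:**

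- Upper dose: 440 × (24 ÷ 12) = 440 × 2 = 880 mg/day
- Lower dose: 220 × (24 ÷ 12) = 220 × 2 = 440 mg/day
- Mixed day: 440 + 220 = 660 mg/day

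Neither end of the range, repeated as scheduled, gives 660. Of these, only the mixed day does, and the row does not describe one. Excess at the upper dose: 880 − 660 = 220 mg; 220 ÷ 660 = 33%.

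**The same check on every row with a daily maximum:**

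| Row | Upper dose, longest or only interval | Upper dose, shortest interval | Lower dose, shortest interval | Stated maximum |
|---|---|---|---|---|
| Acetaminophen | 1000 × 4 = 4000 | 1000 × 6 = 6000 | 500 × 6 = 3000 | 4000 |
| Ibuprofen | 800 × 3 = 2400 | 800 × 4 = 3200 | 400 × 4 = 1600 | 2400 |
| Naproxen | 500 × 2 = 1000 | same (one interval) | 250 × 2 = 500 | 1000 |
| Naproxen sodium | 440 × 2 = 880 | same (one interval) | 220 × 2 = 440 | 660 |

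(All in mg/day.)

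In three of the four rows the maximum equals the upper dose at the longest or only listed interval. Naproxen sodium breaks that pattern: its upper dose exceeds the maximum at every interval the row lists.

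**The case against.** The best answer to the point is that a maximum is a limit and not a product of the other columns. Read that way, the row can be followed: 220 + 220 = 440 mg and 440 + 220 = 660 mg both satisfy every entry, and a prescriber is expected to read the whole row. This part stands. It would be wrong to say that a 440 mg dose can never be given; what breaches the limit is 440 mg at both 12-hour points. It does not remove the inconsistency, because the row gives one interval and no rule for lowering the second dose, so the reader has to supply an uneven schedule that is not written down.

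Two stronger readings are tempting and should be resisted.

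First, a reader might infer that the acetaminophen and ibuprofen rows fail as well, since 1000 mg every 4 hours gives 6000 mg and 800 mg every 6 hours gives 3200 mg. The documents do not support that. Those rows give a range of intervals as well as a range of doses, and the maximum does the ordinary work of limiting how the two combine. Each is met exactly by the upper dose at the longer interval, and the lower dose at the shorter interval falls below it.

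Second, a reader might infer that subjects would be overdosed or harmed. The documents do not show this either. They say nothing about the consequence of 880 mg in a day. Prescribing rests with the PI or designees, the maximum is printed in the same row, and Protocol 10.2 states that medical staff are on the unit at all hours. The table is introduced as a list of commonly used medications and is not described as a standing order set.

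**Conclusion.** The point holds for one row. In the naproxen sodium entry, the listed upper dose at the only listed interval comes to 880 mg/day, 220 mg (33%) above that row's maximum of 660 mg/day, and nothing in the protocol or SAP resolves the difference. The conclusion assumes that every 12 hours means two doses in 24 hours and that the dose range applies at each time point, which is how the row reads on its face. If a reader takes the maximum as overriding the dose range, the row is workable but still leaves the second dose unspecified after a 440 mg dose.

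The acetaminophen, ibuprofen and plain naproxen rows are consistent with their own maxima and are not part of the finding. The matter is minor. It concerns the clarity of a dosing instruction and the judging of deviations; it does not touch the primary endpoint, any secondary endpoint, the sample size or a planned analysis. No view is taken on whether the dose, the interval or the maximum is the entry that should change.

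**What to change.** The sponsor and investigator should reconcile the dosage and maximum entries of the naproxen sodium row in Protocol 9.4.8.2, so that the upper dose given at the listed interval and the daily maximum agree. If the maximum is meant to override the dose range, the row should say so explicitly. Which entry changes is a clinical decision for them. The other rows can stay as they are.

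The cost is a one-row protocol clarification, which can be carried in the next amendment. The SAP needs no change, because it does not reproduce the table and no analysis depends on it.
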